8.7.1 Adverse Event Reporting

An adverse event that is not serious or related to the study drug or drug delivery device is to be reported to the designated Medical Monitor within 10 working days of the Investigator first becoming aware of the event. Notification will occur by recording on the appropriate CRF(s), scanning and email or faxing the CRF(s) of the visit in which the event is first noted. An adverse event is also to be reported to the reviewing IRB/IEC per their reporting requirements.

8.7.2 Serious Adverse Event Reporting

All SAEs, regardless of cause(s) or relationship to the study drug or the drug delivery device, must be reported within 24 hours of becoming aware of the event to the designated Medical Monitor by telephone, facsimile, or email. Additional contact numbers and AE/SAE reporting information will be provided to each site in a separate document.

All SAEs will be reported to:

[name]
Mati Therapeutics Inc.
[contact]
[contact]
[contact] (cell)
[contact]

The Investigator must complete the SAE Report Form and send it with other relevant pages of the CRF to the designated Medical Monitor within 24 hours of discovery of the SAE. The Investigator will also compile with urgent priority other relevant documentation (copies of test results, hospital discharge summary, autopsy report, etc.) and send this information to the designated Medical Monitor. Any SAE will be reported to the Investigator's IRB/IEC per their reporting requirements.

8.7.3 Unanticipated Problem Reporting

If during the study an adverse event occurs that may reasonably be regarded as study drug and/or study-device-related and was not previously expected in nature, severity, or degree of incidence in the investigation plan, the Investigator is to report the unanticipated adverse event to the designated Medical Monitor within 48 hours, and to the Investigator's IRB as soon as possible, but no later than 10 working days, after learning of the event as required by 21CFR812.

8.7.4 Events of Special Interest

N/A

8.7.5 Unmasking Study Treatment

Masked information on the identity of the assigned test article will be provided for each study subject. If the treatment code needs to be broken in the interest of the study subject's safety, the Investigator is encouraged to contact the Medical Monitor prior to unmasking if there is sufficient time. Dependent upon the individual circumstances (i.e., medical emergency), the individual code may be broken prior to contact with the Medical Monitor. The Medical Monitor must be informed in all cases in which the code was broken and of the circumstances involved.

The Medical Monitor for this study is: [name]
[contact] (office)
[contact] (cell)

Additionally, the Medical Monitor may be required to unmask a study subject's masked treatment if the AE meets criteria of a Suspected Unexpected Serious Adverse Reaction (SUSAR) in order to fulfill expedited regulatory reporting requirements.

8.8 Study Halting Rules

Collaboration between representatives of Mati Therapeutics Inc., Investigators and statisticians may stop the study if there is evidence of a lack of safety or efficacy associated with the study drug/device or if there is sufficient evidence of efficacy to warrant phase III testing.

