3 OBJECTIVES AND PURPOSE

To evaluate the safety and efficacy of N-PPDS in the treatment of post-operative ocular pain and inflammation associated with cataract surgery.

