4.2 Study Endpoints

The study will be complete when 75 study subjects (75 eyes) have been evaluated at Visit 7 (Day 14 post-op) or have been terminated from the study.

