10.4.7 Planned Interim Analyses

An interim analysis will be performed to confirm that positive efficacy trends are being observed and that the enrolment should continue. The interim analysis will be performed after a minimum of 25 subjects have completed visit 7 in the study. The data will be unmasked and analysis of primary and secondary endpoints will be completed along with baseline descriptive statistics.

Sites will remain masked to treatment for the remainder of the study. A summary of the results may be shared with the sites but no individual site data will be generated or shared.

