10.6.1 Enrollment/ Randomization/Masking Procedures

Randomization will be stratified (or balanced) by study center. Patients will be randomized in a ratio of 2:1, 2 active (N-PPDS) for each placebo (p-PPDS). Treatment assignments for this study have been randomized in blocks of three (each sequential group of three, two lines are active treatment, and one line is placebo treatment), 25 blocks total. Using a random number generator (JMP 10.0 statistical software), each block is assigned three randomized numbers. The dataset is then sorted by ascending order by block, by random number. By ascending order, each line is assigned a subject number (e.g. 101-175). As a subject qualifies for enrollment, they will be sequentially assigned a subject number. The subject numbers designated what treatment group the subject will be assigned.

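### Section 8.8 allows a stop for efficacy with no boundary, alpha allocation or minimum exposure, and the plan does not say whether a favourable interim under 10.4.7 continues or ends enrolment

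*Combined protocol and SAP*

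**What the plan says.** Section 8.8 gives a group of sponsor representatives, investigators and statisticians three grounds for ending the study. Two are adverse: the group "may stop the study if there is evidence of a lack of safety or efficacy associated with the study drug/device". The third is favourable: it may also stop "if there is sufficient evidence of efficacy to warrant phase III testing". No statistic, endpoint, threshold or minimum number treated is attached to any of them.

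Section 10.4.7 plans one interim analysis. Its stated aim is "to confirm that positive efficacy trends are being observed and that the enrolment should continue". On timing: "The interim analysis will be performed after a minimum of 25 subjects have completed visit 7 in the study". On content: "The data will be unmasked and analysis of primary and secondary endpoints will be completed along with baseline descriptive statistics". Safety endpoints are not listed, and no criterion is given for a positive trend.

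Elsewhere, 10.4.1 sets a two-sided 5% level for all tests, 10.4.8 marks multiplicity as not applicable, and 10.5 reports no sample size calculation because this is a pilot. Section 4.2 defines ordinary completion: "The study will be complete when 75 study subjects (75 eyes) have been evaluated at Visit 7", or have been terminated from the study. Section 3 gives safety and efficacy equal standing: "To evaluate the safety and efficacy of N-PPDS in the treatment of post-operative ocular pain and inflammation". Sections 8.8 and 10.4.7 do not refer to each other.

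**The concern.** The interim in 10.4.7 is the only planned occasion on which unmasked efficacy results will exist before the end, so it is where the efficacy limb of 8.8 would most naturally be used. A good result there could be called a trend, and enrolment would continue, or sufficient evidence, and the study would end. The choice would be made after the results are known.

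Three things are at stake:

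- **The estimate.** Stopping because an early result looks good selects overestimates, and by the wording of 8.8 that estimate would go into Phase III planning.
- **The error rate.** A second test at 5%, with no allocation, raises the chance of a false positive claim.
- **Safety exposure.** The efficacy limb requires no minimum number on N-PPDS. The interim lists no safety endpoints, and under 8.9 the Medical Monitor stays masked until the study is complete. As written, an efficacy stop would not require a comparative safety review.

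**Working it through.** **1. The plan's own split.** 75 × 2/3 = 50 N-PPDS and 75 × 1/3 = 25 p-PPDS, as in 4.1; 25 blocks of three (10.6.1) give the same.

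**2. Split at the minimum trigger.** 25 × 2/3 = 16.7 and 25 × 1/3 = 8.3, so about 17 v 8. With blocks of three in one to three centres, 15 to 18 of the first 25 randomised could be on N-PPDS. The information fraction is 25/75 = 1/3.

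**3. Estimate among trials that stop.** The plan states no criterion, so I assume two-sided p<0.05 in favour of N-PPDS on the no-pain/pain tabulation of 10.4.9 at a single visit. Illustrative rates are those of topical nepafenac: about 80% v 50% at Day 1, and 86% v 46% and 84% v 38% at Day 14 (section 2.1; Appendix 5, section 14). The 65% v 50% row is an assumed weaker effect. For every pair (x, y) of pain-free counts, d = x/n1 − y/n0; the mean of d is taken over pairs with p<0.05 and d>0, weighted by their binomial probabilities. Each cell gives pooled chi-square / Fisher.

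| True rates (difference) | Chance of p<0.05 at 17 v 8 | Mean reported difference, 17 v 8 | Mean reported difference, 50 v 25 |
|---|---|---|---|
| 80 v 50 (30) | 37% / 22% | 50.1 / 56.5 | 34.6 / 35.9 |
| 86 v 46 (40) | 61% / 43% | 52.0 / 57.6 | 41.1 / 41.5 |
| 84 v 38 (46) | 68% / 52% | 56.1 / 60.8 | 46.4 / 46.7 |
| 65 v 50 (15) | 11% / 6% | 50.8 / 55.7 | 30.1 / 31.7 |

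For 80 v 50 the inflation is 50.1/30 = 1.67 to 56.5/30 = 1.88 at 17 v 8, against 34.6/30 = 1.15 to 35.9/30 = 1.20 at 50 v 25. The right-hand column is the fair comparator, because selecting on significance inflates the full-size trial as well.

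**4. Type I error.** For one test at both looks, take Z1 and Z2 as bivariate normal with correlation √(1/3) = 0.577. Then 1 − P(|Z1|<1.96 and |Z2|<1.96) = 0.088 two-sided. Counting only the favourable direction it is 0.044, against a nominal 0.025. With p<0.001 (|Z|>3.29) at the interim and p<0.05 at the end, the two-sided total is 0.0505.

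**5. What a p<0.001 boundary does to the estimate.** The enumeration of step 3 with p<0.001 at 17 v 8 and true 80 v 50 gives a stop in 3.9% (chi-square) or 1.5% (Fisher) of trials, with mean reported differences of 72 and 79 points. The boundary protects alpha and makes a stop rare, but it does not make the estimate from a stopped trial usable.

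**6. Safety.** With no event seen, the one-sided 95% upper bound is 1 − 0.05^(1/n): 16.2% at n = 17 and 5.8% at n = 50. The chance of at least one case of a 5% harm is 1 − 0.95^n: 58% and 92%.

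**7. Exposure above the floor.** Enrolment need not pause for the interim. Assume 75 subjects enter evenly over 20 to 24 weeks (the synopsis projects about six months in all), with about 2.3 weeks from Visit 2 to Visit 7. Then 75/24 × 2.3 = 7 to 75/20 × 2.3 = 9 more subjects have a plug when the 25th completes. That is 32 to 34 subjects in total, about 22 of them on N-PPDS. The bound becomes 1 − 0.05^(1/22) = 12.7%, and detection of a 5% harm 1 − 0.95^22 = 68%.

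**The case against.** The strongest reply is that there is no contradiction. A trend and evidence sufficient for Phase III are different levels of proof, 8.8 is permissive and does not mention the interim, and 4.2 describes ordinary completion without barring an early stop. Ending a Phase 2 pilot early to move on is also a legitimate sponsor choice. This stands as far as it goes: a reader might infer that the sections contradict each other, and the text does not support that. The gap is that neither standard is defined and nothing orders the two.

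Several other stronger readings are tempting and also fail.

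- A reader might take 17 as the N-PPDS safety exposure at a stop. It is the approximate figure at the minimum trigger. Section 10.4.4 counts every exposed subject, so about 22 is plausible, and more if data cleaning takes time.
- A reader might say the safety objective would go unanswered. The plan sets no precision target for safety, and 50 subjects is also few: 0.99^50, or 61%, is the chance of seeing no case of a 1% event.
- A reader might argue that waiting costs only a 14-day follow-up. At 25 completers up to 50 subjects may still have to be enrolled or followed, about 17 of them on placebo with NSAIDs and corticosteroids restricted. The option has real value to the sponsor.
- A reader might set 50 to 57 points against the true 30. The contrast attributable to stopping early is with the 35 to 36 points that significant full-size trials report.

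It is also fair to say that the p<0.05 trigger is assumed, that 10.4.2 defines the primary variable as pain severity at four visits rather than a pain-free rate at one, and that topical rates may not carry over to a plug. The size of the bias therefore depends on assumptions; its direction is the same in every case tried.

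**Conclusion.** The point holds as a gap between 8.8 and 10.4.7, not as a contradiction. A favourable interim could be used to continue or to stop, on undefined standards, after unmasking.

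If it were used to stop at about 17 v 8 under an assumed p<0.05 trigger and true rates of 80% v 50%, the reported effect would average 50 to 57 points, against 35 to 36 among significant trials at 50 v 25. At the Day 14 rates the excess over full size is smaller, roughly 10 to 16 points. If the final test is also run at 5%, overall two-sided alpha is about 0.088 for a single test, before the four visits are considered. The zero-event upper bound would be up to 16% at the floor, or about 13% with the enrolment pattern assumed above, rather than 5.8%. On the topical rates the trigger would be met in 22% to 68% of trials, so this is not a remote case.

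The alpha figure and the safety bounds do not depend on the assumed pain-free rates; the exaggeration figures do.

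**What to change.** Delete the favourable-efficacy ground from 8.8, leaving the halting grounds for lack of safety and lack of efficacy. State in both 8.8 and 10.4.7 that a favourable interim does not end enrolment, which continues to 75 as in 4.2. Add that any interim estimate used to begin Phase III planning is provisional until the full data are in.

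If the sponsor wishes to keep an efficacy stop, name one endpoint at one visit and a stringent boundary, for example Haybittle-Peto at p<0.001, which leaves the final 5% test essentially intact (0.0505 overall). Step 5 shows why the provisional label on the estimate matters even more in that case.

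The change is one clause removed and two or three sentences added, with no subjects beyond the plan. The sponsor gives up, or restricts, the option of not enrolling up to 75 − 25 = 50 already planned subjects, about 25 − 8 = 17 of them on placebo. Its general right to terminate in 5.5 and 5.6 is unchanged, so the fix removes an undefined efficacy rule and not the power to stop.

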8.9 Safety Oversight

This study will utilize a Medical Monitor for safety monitoring. The Medical Monitor will remain masked regarding the study treatment until the study has been completed. The Medical Monitor will review and assess any reports of adverse events and, if necessary, to discuss these with the reporting Investigator(s). The medical monitor will also be available to answer all questions from Investigators.

9 CLINICAL MONITORING

Mati Therapeutics Inc. representative will ensure that the investigation is conducted in accordance with the following:

- a. GCPs as specified in ICH E6 (R1) and E8 (8.2) and 21 CFR. Part 50, 54, 56 and 312
- b. The signed Investigators' Agreement
- c. The signed protocol for the study
- d. Any conditions imposed by the IRB
- e. The requirements of the regulations for the Protection of Human Patients (21CFR50) and all other applicable regulations

Prior to initiation of the study at a site, the CRA will conduct a visit with the Investigator(s) and the study staff to ensure the following

- a. The Investigator understand the investigational status of the study material and the requirements for its accountability
- b. The Investigator understands the protocol and understands and accepts their obligations in conducting the clinical investigation
- c. The Investigator has adequate facilities for conducting the study, and equipment and instrumentation required by the protocol
- d. The Investigators and their staff have sufficient time and access to an adequate number of subjects to conduct the clinical investigation.

During the course of the investigation, the CRA will conduct periodic site visits and maintain telephone contact with the Investigators and their staff to ensure that the study is being conducted in accordance with the protocol, and with any specific conditions of the IRB and

clinical requirements. At such visits, the CRA will ensure that informed consent has been obtained and documented for each study subject, in accordance with 21 CFR parts 50 and 56, and the requirements of the overseeing IRB and the Sponsor. The CRA will review and compare CRFs to source records and supporting documents to ensure that data recorded on the CRFs are complete, accurate, and legible, and that any corrections to the CRFs are made with a single line strike-through of the incorrect entry, and entry of the correct information adjacent with initials of the individual making the correction and date of corrected entry. The CRA will further ensure that there are no data omissions and that any study subject withdrawals are documented. The CRA will review CRFs and source records for any unanticipated AEs, and ensure that the Investigators are complying with FDA and Sponsor requirements for reporting AEs and SAEs. The CRA will ensure that the Investigators are carrying out the agreed upon activities and have not delegated them to unauthorized staff, that the facilities and staff continue to be acceptable for the study, and that the Investigators are properly tracking study inventory and are accounting for the disposition of all study drug.

The CRA shall prepare and maintain records of each site visit, significant telephone discussion, and written communications with the site. These records will include such information as:

- a. Date, name, and address of the Investigators and names of other staff members present at each meeting
- b. A summary of the findings of the visit
- c. A statement of any action taken by the CRA or Investigators to correct any deficiencies noted.

10 STATISTICAL CONSIDERATIONS

10.1 Statistical and Analytical Plans

The primary analysis population will be an ITT (Intent-to-Treat) analysis for all study subjects randomized to treatment that have completed at least one post-operative follow-up visit and had no major protocol violations. Individual study subjects or individual visits may be excluded if a major protocol violation occurs (such as violation of inclusion/exclusion criteria, the use of prohibited medications or non-compliance with protocol requirements that can potentially have significant impact on efficacy).

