10.4.2 Analysis of the Primary Efficacy Endpoint(s)

The primary efficacy variable will be the severity of ocular pain report at visit 4, 5, 6 and 7 (post-op days 1, 3, 7 and 14). For analyses using the intent-to-treat (ITT) data set, all data from all subjects with at least one post-operative follow-up pain evaluation will be included. For the per protocol (PP) analyses dataset, data from subjects or visits with significant protocol deviations will be excluded.

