10.4.3 Analysis of the Secondary Endpoint(s)

The secondary efficacy variable will be the severity of ocular inflammation (anterior chamber cells and flare) report at visit 4, 5, 6 and 7 (post-op days 3, 7 and 14). For analyses using the intent-to-treat (ITT) data set, all data from all subjects with at least one post-operative follow-up inflammation evaluation will be included. For the per protocol (PP) analyses dataset, data from subjects or visits with significant protocol deviations will be excluded.

Efficacy analysis of primary and secondary endpoints will be based on observed data only. In the case of a significant amount of missing data, Last Observation Carried Forward may be used for sensitivity analysis.

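### The primary ITT population excludes major protocol violators in Section 10.1 but keeps them in Sections 10.4.2 and 10.4.3, and nothing says which definition governs

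*Combined protocol and SAP*

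**What the plan says.** Section 10.1 names ITT as the primary analysis population and defines it as the analysis "for all study subjects randomized to treatment that have completed at least one post-operative follow-up visit and had no major protocol violations". Its next sentence adds that "Individual study subjects or individual visits may be excluded if a major protocol violation occurs", and lists eligibility violations, prohibited medication and non-compliance as examples.

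Section 10.4.2 (pain, primary) describes the ITT data set differently: "all data from all subjects with at least one post-operative follow-up pain evaluation will be included". Exclusions go elsewhere: "For the per protocol (PP) analyses dataset, data from subjects or visits with significant protocol deviations will be excluded". Section 10.4.3 (inflammation, secondary) repeats the pattern: in the ITT set "all data from all subjects with at least one post-operative follow-up inflammation evaluation will be included", and deviations are again handled in the PP set.

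The data rule for both endpoints is in Section 10.4.3: "Efficacy analysis of primary and secondary endpoints will be based on observed data only". If much is missing, "Last Observation Carried Forward may be used for sensitivity analysis".

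Section 10.4.7 plans an interim analysis once at least 25 subjects have completed Visit 7: "The data will be unmasked and analysis of primary and secondary endpoints will be completed along with baseline descriptive statistics".

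**The concern.** Absence of a major violation is a condition of ITT membership in one section and plays no part in ITT in the other two. Two statisticians working from this protocol could build different primary data sets, and each could cite a section in support. If Section 10.1 is followed, the primary and PP sets nearly coincide (provided that the two undefined deviation terms mean much the same), and the reader never sees an analysis that keeps all the evaluated subjects.

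The exclusions are also not all neutral. Section 7.9 treats medication for pain or inflammation given outside the rescue criteria as prohibited and as a protocol deviation, and Section 10.1 lists prohibited medication as grounds for exclusion. Leaving the set can therefore depend on the outcome being measured. The scope is limited: under Section 7.9.1, moderate to severe pain, or cells or flare of grade 3 or more, qualifies for permitted rescue, so this route concerns treatment below those thresholds.

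Finally, if the definition is still open at the interim, it could be chosen with unmasked results known.

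**Working it through.** **The texts side by side**

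| | Section 10.1 | Sections 10.4.2 and 10.4.3 |
|---|---|---|
| Entry to ITT | Randomized, at least one completed post-operative visit | At least one post-operative evaluation of the endpoint |
| Violators in ITT | Out (first sentence); may be excluded (second sentence) | In, with all their data |
| Where exclusions belong | The primary ITT set | The PP set |
| Trigger | Major protocol violation | Significant protocol deviation |

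Test case: a subject has a Day 1 pain score and later takes a prohibited medication that is judged a major violation. Under Section 10.4.2 the subject and all observed data are in ITT. Under the first sentence of Section 10.1 the subject is out.

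No other section decides the matter. Section 10.3, although headed Analysis Datasets, defines no population. Section 10.6.3 provides for a review of subjects and visits before code break but does not say which definition that review applies. The different trigger terms do not reconcile the sections, because neither is defined beyond examples and Sections 10.4.2 and 10.4.3 keep all data in ITT.

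**Illustration of size.** The plan gives no exclusion rate, efficacy test or power, so there is no figure to reproduce.

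Inputs from the documents:
- arms of 50 and 25 (Section 4.1) and a two-sided 5% level (Section 10.4.1)
- the pain-free yes/no split (Section 10.4.9)
- Day 1 pain-free rates of about 80% and 50% for topical nepafenac 0.1% and vehicle (Section 2.1)

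Assumptions: a share *g* of subjects with pain is excluded, and a Fisher exact test is used.

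After exclusion, the pain-free rate in an arm with true rate *p* is p / (1 − (1 − p)g).

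*Equal exclusion in both arms.* Subjects with pain: 50 × 0.20 = 10 active and 25 × 0.50 = 12.5 placebo, 22.5 in total.

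| g | Excluded (22.5 × g) | Active | Placebo | Difference |
|---|---|---|---|---|
| 0 | 0 | 80.0% | 50.0% | 30.0 points |
| 5% | 1.13 | 0.80/0.99 = 80.8% | 0.50/0.975 = 51.3% | 29.5 points |
| 10% | 2.25 | 0.80/0.98 = 81.6% | 0.50/0.95 = 52.6% | 29.0 points |
| 20% | 4.50 | 0.80/0.96 = 83.3% | 0.50/0.90 = 55.6% | 27.8 points |

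*Exclusion in one arm only.*
- g = 10%: placebo only, 80.0 − 52.6 = 27.4 points; active only, 81.6 − 50.0 = 31.6 points.
- g = 20%: placebo only, 80.0 − 55.6 = 24.4 points; active only, 83.3 − 50.0 = 33.3 points.

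*Opposite conclusions* (p ≤ 0.05 in one set only), 200,000 simulated trials per setting with equal exclusion of 5/10/20%: 4.7/7.8/12.4% of trials. Power by exact enumeration is 69.1% in the full set and 68.9/67.6/63.8% in the reduced set.

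*No true effect* (50% pain-free in both arms), same exclusions: the false-positive rate is 4.1% in the full set, 4.1/4.1/3.7% in the reduced set, and 4.7/5.0/5.2% if significance in either set were accepted. There is no material inflation.

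*At the interim minimum* of 25 subjects (about 17 and 8), excluding one placebo subject with pain moves that arm from 4/8 = 50% to 4/7 = 57% pain-free.

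**The case against.** The best case on the other side is that this is a clarification with little numerical consequence.

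- **Pilot study with both sets planned.** Section 10.5 states no sample size basis, and Section 10.4.2 provides for both ITT and PP, so both results would probably be visible. But the plan also states hypotheses, tests at 5%, and uses the interim to decide whether enrolment continues. Those decisions need one population.
- **Masked classification.** Section 10.3 defers unmasking until data are verified and classifications assigned, and Section 10.6.3 reviews subjects and visits before code break. This limits outcome-driven selection. It does not say which definition applies, and Section 10.4.7 does not say how these safeguards work at the interim.
- **Section 10.1 leaves discretion.** Its second sentence is permissive. That is true, but its first sentence is not, so the section is also loose within itself.
- **Neither definition is a full ITT set.** This stands. Sections 10.4.2 and 10.4.3 still drop randomized subjects without a post-operative evaluation, such as some who are discontinued for surgical complications and replaced (Sections 5.3 and 5.5.2.2). The choice is between two modified sets.
- **Exit rules shrink the gap.** Users of prohibited therapy may leave the study (Sections 5.5.1.2 and 7.7.1), so under the observed-data rule the two sets may differ mainly on visits before exit. This also stands, and it is a further reason to read the figures as illustrative.
- **Opposite conclusions are not all bias.** Removing the same number of subjects regardless of outcome gives opposite conclusions in roughly 3%, 5.5% and 9% of trials, about 70% of the figures above. Most of that instability comes from losing any few subjects from a trial of 75.

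**Conclusion.** The contradiction is real, sits in the primary analysis population, and is not resolved anywhere in the document. It must be fixed. As written, Section 10.1 labels as ITT a set that is per-protocol in substance, with exclusions that can depend partly on pain or inflammation.

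The likely numerical effect is modest. With equal exclusion of 5 to 10% of subjects with pain, the 30-point Day 1 difference moves by 1 point or less, and false positives do not rise materially. Unequal exclusion of 20% could move it to anywhere between 24.4 and 33.3 points. These figures assume topical-nepafenac rates for the plug, a Fisher test and invented exclusion shares. The conclusion depends on none of them: it follows from the three sections alone.

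**What to change.** Before the interim unmasking in Section 10.4.7:

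1. In Section 10.1, delete the condition about major protocol violations and move the sentence on excluding subjects or visits to the PP definition.
2. Use one ITT definition throughout, built on Sections 10.4.2 and 10.4.3: all randomized subjects with at least one post-operative evaluation of the endpoint, all observed data, analysed as randomized. The words on randomization are an addition to those two sections.
3. Use one defined term for the deviations that lead to PP exclusion.
4. Report by arm the randomized subjects who have no post-operative evaluation.

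The observed-data rule and the optional LOCF sensitivity analysis need no change for this point. Separately, Sections 7.7.1 and 7.9 (with 7.9.1) must be reconciled on corticosteroid use, since they affect what counts as prohibited; no position is taken here on which should stand.

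The cost is one clause deleted, one sentence moved, one term defined and a short by-arm count. A few ineligible or non-compliant subjects stay in the primary set, and the PP analysis shows the result without them.

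### Section 10.1 defines the primary ITT set in per-protocol terms, contradicting the ITT definition in 10.4.2 and 10.4.3

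*Combined protocol and SAP*

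**What the plan says.** Section 10.1 names ITT as the primary analysis population and restricts it to a set "for all study subjects randomized to treatment that have completed at least one post-operative follow-up visit and had no major protocol violations". The next sentence adds that "Individual study subjects or individual visits may be excluded if a major protocol violation occurs", and its examples include "the use of prohibited medications or non-compliance with protocol requirements".

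Section 10.4.2 says of the same ITT data set, for pain, that "all data from all subjects with at least one post-operative follow-up pain evaluation will be included". It gives the exclusions to the per-protocol set, where "data from subjects or visits with significant protocol deviations will be excluded". Section 10.4.3 repeats the arrangement for inflammation: in ITT, "all data from all subjects with at least one post-operative follow-up inflammation evaluation will be included", with the same PP exclusion.

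Other provisions that bear on the point:

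- Primary variable (10.4.2): "The primary efficacy variable will be the severity of ocular pain report at visit 4, 5, 6 and 7".
- Missing data (10.4.3): "Efficacy analysis of primary and secondary endpoints will be based on observed data only", with last observation carried forward as an optional sensitivity analysis.
- Rescue (7.9, 7.9.1): prednisolone acetate 1% is allowed for cell or flare grade 3 or more, or moderate to severe pain. Medication given when those criteria are not met counts as prohibited.
- General ban (7.2.2, 7.7.1): post-operative NSAIDs and corticosteroids are prohibited, with no stated exception for rescue. Under 7.7.1 a subject who needs one is terminated and followed to Day 14.
- Timing (10.3, 10.6.3, 10.4.7): subjects and visits are classified before the code is broken, but the data are unmasked for an interim analysis once at least 25 subjects have completed Visit 7.

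**The concern.** The primary population carries one name and two definitions. Two analysts following the plan could build different primary data sets and both claim to have followed it.

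The difference is not neutral bookkeeping. A subject who takes a steroid or NSAID for ocular pain or inflammation does so because of how the eye is doing, which is what the trial measures. Such use is plausibly more common on placebo. A primary set that removes these subjects or visits selects on an event that follows randomization and is related to the outcome, so the protection that randomization gives to the comparison is weakened. The result also feeds the interim analysis, which is meant to inform whether enrolment continues, and the two-sided 5% tests in 10.4.1.

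**Working it through.** **1. The two definitions side by side**

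| | 10.1 | 10.4.2 and 10.4.3 |
|---|---|---|
| Name | ITT, primary | ITT |
| Entry | randomized, at least one post-operative visit, no major violation | at least one post-operative pain (or inflammation) evaluation |
| Exclusion for violations | yes: subjects or visits | none in ITT; placed in PP |
| Prohibited medication | named as a ground | not named for ITT |

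The 10.1 column matches what 10.4.2 and 10.4.3 call PP. The terms differ (major violations against significant deviations), and neither has a decision rule beyond the examples in 10.1. Section 10.1 is also not uniform within itself: its first sentence makes absence of violations a condition of entry, while its second makes exclusion discretionary.

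**2. Who is reached**

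Off-criteria steroid or NSAID use is clearly reached, since 7.9 classes it as prohibited. On-criteria rescue is unclear: 7.9 allows it, but 7.2.2 and 7.7.1 carry no rescue exception.

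**3. Illustration of size**

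The plan states no effect size, power or rate of steroid use, so there is no figure of its own to reproduce. Inputs:

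- n = 50 active and 25 placebo (4.1).
- Assumed Day-14 pain-free rates p = 0.86 and 0.46, from one label study of nepafenac 0.3% drops (2.1; Appendix 5). That study's denominator is all randomized subjects, so not every failure was necessarily seen in pain.
- Every excluded subject is assumed to be in pain at Day 14.

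Excluding k such subjects from an arm of n gives rate = p × n / (n − k). With no exclusion the difference is 86.0 − 46.0 = 40.0 points.

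| Excluded, active / placebo | Active | Placebo | Difference |
|---|---|---|---|
| 0 / 1 | 86.0% | 11.5/24 = 47.9% | 38.1 |
| 0 / 2 | 86.0% | 11.5/23 = 50.0% | 36.0 |
| 0 / 3 | 86.0% | 11.5/22 = 52.3% | 33.7 |
| 1 / 1 | 43/49 = 87.8% | 47.9% | 39.8 |

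(11.5 is the expected placebo count, 0.46 × 25.)

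The loss from one placebo exclusion is p/24: 1.6, 1.9 and 2.5 points for p = 0.38, 0.46 and an assumed 0.60. At an interim of about 17 active and 8 placebo (25 subjects split 2:1, assumed), it is p/7: 5.4, 6.6 and 8.6 points.

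**4. Direction**

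If a share f of subjects with pain is excluded, rate = p / (1 − (1 − p)f).

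- 10% of active and 25% of placebo: 87.2 − 53.2 = 34.0 points.
- 25% in both arms: 89.1 − 53.2 = 35.9 points. The odds ratio is unchanged at 7.21.
- 25% of active and 10% of placebo: 89.1 − 48.6 = 40.5 points.

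The difference therefore shrinks when exclusion is equal across arms or heavier on placebo, but it can grow if exclusion is heavier on active.

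**The case against.** Several objections carry weight.

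- **Post-steroid scores.** A reader might infer that the plan has no rule at all for scores recorded after a steroid. The documents do not support that. All data in ITT, together with analysis of observed data only, keeps those scores by default. What is absent is an explicit statement about rescue, and which strategy to adopt is the sponsor's choice.
- **Narrow reach.** A reader might also infer that 10.1 removes rescued subjects generally. It clearly reaches only use outside the rescue criteria. The specific rescue section can reasonably be read as overriding the general ban, and the argument that use follows the outcome is strongest for the on-criteria group, whose status is unclear.
- **Demonstrated bias.** The figures concern Day-14 pain-free proportions from eye-drop studies, not the severity variable that 10.4.2 makes primary. They drop whole subjects; visit-level exclusion is not modelled. With one or two exclusions the final effect is small, and the likely direction is against the product. A biased primary result is not shown.
- **Masked classification.** Sections 10.3 and 10.6.3 limit exclusions made with knowledge of arm. That stands. They supply no criteria, however, and cannot remove a difference between arms in the medication use itself. Subjects evaluated after the interim would also be classified after data have been unmasked once.
- **Disposition.** A reader might see a flat conflict between 7.7.1 (terminated, not replaced) and 5.5.1.2 (discontinued, replaced). These can be read as separate triggers: a drug that is required against one that has been used. The remaining gap is that 7.9.1 does not say whether a rescued subject is terminated under 7.7.1.

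None of this reconciles 10.1 with 10.4.2 and 10.4.3. The pilot label does not help either, because the plan still specifies hypothesis tests and an interim look at the same endpoints.

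**Conclusion.** The point holds, as wrong as written. The primary set has two incompatible definitions, and the one in 10.1 is a per-protocol set under an ITT name. Its exclusions can depend on medication use after randomization that is related to the outcome: clearly so for off-criteria steroid or NSAID use, uncertainly for on-criteria rescue.

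The conclusion rests on the text alone. The magnitude is unknown. Under the assumed rates, the illustrations run from almost no change (39.8 against 40.0 points) to a loss of 6.3 points with three placebo exclusions and none on active (40.0 − 33.7). One placebo exclusion at an assumed 17/8 interim would cost 5.4 to 8.6 points. These are sensitivities for a pain-free proportion. They do not predict bias in the severity variable.

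**What to change.** **Change.** In 10.1, delete for the primary set both the condition that subjects had no major violations and the sentence permitting exclusion of subjects or visits. State that the primary ITT set is the one defined in 10.4.2 and 10.4.3, and apply violation-based exclusions only to PP. Settle this before the interim unmasking.

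**Cost.** Wording only: no extra subjects, visits or procedures. The downside is that subjects with violations stay in the primary analysis and reported success rates may fall slightly, mainly on placebo. For example, if three placebo subjects and one active subject with pain are kept rather than excluded, placebo goes from 52.3% to 46.0% and active from 87.8% to 86.0%.

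**Two further suggestions, not needed for the finding.**

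- State how scores after rescue are handled. The default is observed scores; a sensitivity tabulation counting rescued subjects as non-responders would be cheap. The choice can matter. With two placebo steroid users who become pain-free and none on active, the illustrative difference is 40.0 points if they count as non-responders, 36.0 if excluded (86.0 − 11.5/23) and 32.0 if scored as observed (86.0 − 13.5/25). Correcting 10.1 therefore does not by itself give a larger difference; it fixes who is analysed.
- Reconcile 7.7.1 with 7.9.1 on whether a rescued subject is terminated and has the plug removed. The clinical path is for the sponsor to set.
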